4.3 Exclusion Criteria

Patients presenting with any of the following will not be included in the study:

- 1. Participants with safety contraindications to MRI examination (determined by standard clinical screening).
- 2. Participants on hemodialysis or with acute renal failure.
- 3. Participants who are pregnant, lactating or are planning to become pregnant during the study.
- 4. Participants who are planning to farther a child during the study.

4.4 Participants of Reproductive Potential

[figure not shown]
Participants must not be pregnant or lactating at enrollment in the study. UAB standard for screening of pregnant or lactating females is asking the participant if they are lactating, pregnant, or if there is a chance they may be pregnant. If the female answers that there is a chance that she may be pregnant, our standard is to perform an on-site urine HCG pregnancy test. The results of that test are then documented. Participants must also agree to continue to use an effective form of birth control for 6 months after taking the study. Effective birth control includes birth control pills, patch, IUD, condom, sponge, diaphragm with spermicide, or avoiding sexual activity that could cause pregnancy. If a female participant becomes pregnant during the study, she will not participate further in this study.

5.0 STUDY TREATMENTS

Each patient will undergo two DCE-MRI exams according to the timeline detailed in Fig. 5. Patients will be treated by standard-of-care therapy otherwise.

6.0 STUDY PROCEDURE AND SCHEDULE

All participants will be asked not to have caffeinated or alcohol drinks for at least 24 hours prior to imaging. The hematocrit (HCT) of each participant will be measured before imaging, which is an important factor to determine plasma input function (PIF) required for PK parameter quantification (PIF=1/(1-HCT)) (39, 40). Each subject will be instructed to put his/her head with the phantoms as shown in **Fig. 6**.

The phantom package will be thoroughly sanitized prior to each use. MRI scanner is equipped with a dual-channel transmit RF coil for improved B₁ field homogeneity. B₀ and B₁ shimming will be conducted, and B₁ mapping will be followed using the vendor's software (41, 42). DCE-MRI acquisition will then be carried out for 5 minutes. Gadoteridol (0.1 mmol/kg) will be injected *i.v.* to each patient at 10 s after the start of imaging procedure and will be followed by a 20-ml saline flush at a constant rate of 2 ml/s. Perfusion phantoms will be infused with 100 mM gadoteridol (0.06 ml/s; 3 ml) at 10 s after imaging start using a syringe pump (NE-1600) that is separate from the contrast agent going into the patient. Prior to DCE-MRI, T₁W images with various flip angles will be obtained for T₁ mapping (43).

7.0 SAFETY

There is minimal physical risk to undergoing the MRI test. Lying supine for 30 minutes to an hour with our phantoms located under the participant could make the participant uncomfortable. As the MRI machine obtains the images for the study, there will be loud noise. There is also a small risk that the patient may be mildly claustrophobic. When gadoteridol (MR contrast agent) is injected into the vein, a cool sensation in the arm or mild nausea is experienced by few patients. A small number of patients may have an allergic reaction to gadoteridol injected into the vein. Gadolinium based MR contrast agents can cause Nephrogenic Systemic Fibrosis (NSF) for patients with severe kidney disease. NSF appears like a bad skin disease, and it can be fatal. However, gadoteridol is known to be safe even in patients with stages 4 and 5 of chronic kidney diseases (44).

The risk of having NSF will be very low. Gadoteridol is classified as the one having the lowest risk of NSF by the European Medicines Agency (EMA) and American College of

Radiology (ACR). In animal studies, gadolinium retention has been found to be extremely low following the repeated administration of gadoteridol, and lowest in brain tissues when compared with gadolinium retention observed after repeated administration of other MR contrast agents (45-47). To our knowledge, no instances of T₁ hyperintensity in the brain have yet been observed following multiple exposure to approved doses of gadoteridol in adult or pediatric patients. In Cho et al's recent study (48), the adverse reactions of gadoteridol injection (up to a triple dose, 0.3 mmol/kg, depending upon the clinical need) were examined in a total of 6163 patients having various diseases. 8 subjects (0.13%) had mild symptoms and 2 subjects (0.03%) had modest symptoms, but not a single serious adverse event was observed. Therefore, the chance of serious adverse events following approved dose (0.1 mmol/kg) of gadoteridol is extremely low among the 12 subjects even after two dosing.

The risks of having significant claustrophobia affecting participation in this study will be low, as participants will be screened for kidney disease, claustrophobia and other conditions that would prevent them from getting an MRI. The risk of pain during insertion of an IV catheter is 100% but minimal and temporary. The risk of nausea during intravenous injection of gadoteridol is less than 1%. The risk of the patient having an allergic reaction to the MR contrast injected intravenously is less than 1%. Allergic reactions to gadoteridol typically do not require medication for reversal. If a patient is uncomfortable during a particular sequence, the exam can be terminated immediately and they will be removed from the MRI machine. During MRI test, earplugs will be given to damp loud noise. Each participant will be closely monitored via microphone while being scanned to detect any risks.

8.0 STATISTICAL METHOD

> Sample Size Justification

Aim 1. The K^{trans} reproducibility measured by the ICC was 0.99 in our previous experiment ($\underline{1}$), when the P4 was used for error correction (3 volunteers x 4 tissues = 12 measurements) (see **Fig. 3C**). For brain DCE-MRI, however, the perfusion value can only be assessed in the tumor region. Thus, to achieve greater than 90% power to confirm that the data repeatability measured by the ICC is larger than 0.9 with 5% type I error, at least 12 volunteers will be needed.

Aim 2. In Yun et al's study (13), the difference of tumor K^{trans} between pseudo- and true-progressions was 91% with the standard deviation (SD) of approximately 50% in each group (p=0.004). If the mean and SD of each group in the proposed study will be the same with those of Yun et al's study (0.44±0.25 vs 0.23±0.10 min⁻¹), the sample size (n=12) will have 55% power at a 5% significant level to differentiate the two groups (assuming n=6 per group) using a one-side two-group student t-test. However, if the SD is reduced to ≤35% using the P4, the power will be increased to ≥90%.

> Statistical Analysis

Descriptive analysis with the mean and SD will be presented for each experimental parameter and each time point. Graphic presentation will be considered when appropriate. Due to repeated measurement, ANOVA analysis with a mixed model will be used to estimate the measurement error (within error) with two-sided 95% confidence interval (49). Data

reproducibility will be assessed using both the ICC and %RDC (33). Tumor PK parameters between pseudo- and true-progressions will be compared using two-group student t-test (50). Data will be transformed using natural logarithms if the variability is found to be dependent upon its mean value. All data will be analyzed using SAS (SAS institute, Cary, NC) by [name] (see her support letter).

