The use of a static phantom comprised of multiple objects with different contrast-agent concentrations was originally suggested to correct the variation in quantitating contrast-agent concentrations of tissues (25). However, a static phantom may not serve as a reliable standard for dynamically changing tissue contrast-agent concentration, because a) the movement of contrast agents in vivo causes additional signal reduction that cannot be replicated by a static phantom, b) the number of data points obtained from a static phantom is small, leading to larger fitting errors, and c) most B₁ mapping techniques are T₁ dependent, thus the nominal flip angle delivered to a static phantom with high contrast-agent concentration cannot be accurately measured, especially in high field MRI (\geq 3T) (26-29). Therefore, a perfusion phantom with a varying contrast-agent concentration is required for accurate correction of MRI system-driven error. A few perfusion phantoms have been developed (30, 31), but these phantoms are too bulky to be simultaneously imaged with a human subject. In addition, these large phantoms are costly and not easily operable by typical MRI technologists, limiting the potential for widespread and routine clinical use. We recently developed a perfusion phantom named P4 (Point-of-care Portable Perfusion Phantom) that significantly reduces variation in quantitating the perfusion of human tissues across different MRI scanners (1). Figure 2A is a photograph of the P4 with its dimensions. is composed of top and bottom chambers with a semi-permeable membrane placed between them. Both chambers are filled with degassed/deionized water before use. After starting DCE-MRI, an MRI contrast agent is infused to the top chamber at a constant rate using a syringe pump. contrast agent displaces the water in the top chamber and diffuses to the bottom chamber as shown Our lab-made software automatically segments the entire region of the bottom chamber (ROI), and the mean value within the ROI is calculated automatically, creating contrast enhancement curves (CEC) as shown in Fig. 2C. The dynamic change of contrast concentration in the bottom chamber was linear for 10 minutes (0.11 mM/min), when independently measured using liquid chromatography-mass spectrometry detection (LC-MS) method (32). repeatability of phantom CEC measured by intra-class correlation coefficient (ICC) (33) was larger than 0.99 in all measurements. Please see our paper for more details (1). The P4 is small enough to be imaged with a human subject and is large enough not to suffer from the partial volume effect, thus MRI system-driven error can be detected during human imaging. correction, the within-subject coefficient of variation (wCV) of the volume transfer constant (Ktrans), a DCE-MRI parameter, was about 20%, but after error correction using the P4, the

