2.2. Secondary goal

To determine whether the reproducibility of quantitative DCE-MRI measurement of glioblastoma can be significantly increased when MRI system-driven error is corrected using the P4 phantom.

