The data reproducibility across two different scanners assesses between-scanner variability combined with the inaccuracy of region of interest (ROI), arterial input function (AIF) and image co-registration. The tumor ROI will be determined by [name] (a neuro-radiologist; co-I) (see "ROI determination" section for the details). The ROIs of two scans of each subject will be matched as closely as possible to minimize intra-observer variation. We recently introduced a novel method to reliably measure individualized AIFs (36) which will be employed in this study. If the patient moves during imaging, a similarity transformation (37) will be used for 3D coregistration. The pharmacokinetic (PK) parameters (e.g., K^{trans}) within the ROI will be averaged at each scan after P4-based error correction, and the mean values of two scans will be compared to calculate the reproducibility coefficient (%RDC) using the equation, %RDC=2.77wCV, where wCV is the within-subject coefficient of variation (38). The %RDC before P4-based error correction will also be calculated for comparison. Data reproducibility will be assessed using the intra-class correlation coefficient (ICC) as well. $ICC = \sigma^2 b / (\sigma^2 b + \sigma^2 w)$, where σb is between-subject standard deviation and σw is within-subject standard deviation.

Each tumor will be classified into pseudo- or true-progression based on the histopathologic data or RANO criteria. We expect approximately 40-50% of glioblastoma will be classified to

pseudo-progression, as demonstrated in previous studies (11-13). All PK parameter maps will be created within a month after image acquisition so that the image processing will not be biased by subsequent clinical findings. We will examine whether the difference of tumor PK parameters between pseudo- and true-progressions will become more statistically significant after P4-based error correction.

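### The secondary goal asks whether P4 correction significantly improves reproducibility, but no planned test, interval or rule addresses the change from uncorrected to corrected data

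*Combined protocol and SAP*

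**What the plan says.** Section 2.2 sets the secondary goal: to determine "whether the reproducibility of quantitative DCE-MRI measurement of glioblastoma can be significantly increased when MRI system-driven error is corrected" with the P4. That is a contrast between corrected and uncorrected measurements.

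The combined protocol and SAP offers three things on reproducibility:

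- Section 8.0, Aim 1 justifies at least 12 subjects by more than 90% power "to confirm that the data repeatability measured by the ICC is larger than 0.9 with 5% type I error". The expected value behind it is the corrected ICC of 0.99 from earlier work.
- Section 8.0, Statistical Analysis, says that "ANOVA analysis with a mixed model will be used to estimate the measurement error (within error) with two-sided 95% confidence interval", and names ICC and %RDC as the measures. It does not say whether the interval is for corrected data, uncorrected data or both.
- Section 3.1 says that, after correction, "the mean values of two scans will be compared to calculate the reproducibility coefficient (%RDC) using the equation, %RDC=2.77wCV". It adds: "The %RDC before P4-based error correction will also be calculated for comparison".

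The one statement about statistical significance before and after correction, at the end of Section 3.1, concerns pseudo- versus true-progression. That is the primary goal.

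Section 1.0 gives the earlier results. Before correction, "the within-subject coefficient of variation (wCV) of the volume transfer constant (Ktrans), a DCE-MRI parameter, was about 20"%, and after it about 4%. The between-scanner ICC rose from 0.89 to 0.99.

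**The concern.** A goal worded in terms of significance needs an inference about the change and a rule for claiming it. The plan gives an absolute threshold for one ICC, an interval for an error and two %RDC values side by side. None of these is a statement about the difference or ratio between corrected and uncorrected data.

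The risk is that what counts as significant improvement is settled after the results are seen. It is greatest if correction helps in tumours but by less than in the earlier work. The 20% and 4% are not glioblastoma figures. Section 3.1 also says that the between-scan comparison carries ROI, arterial input function and co-registration error along with scanner variability, so a smaller reduction is possible.

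**Working it through.** **1. The plan's own figure.** Inputs from Section 8.0 and Section 1.0: n=12, two scans each, null ICC 0.9, expected ICC 0.99, 5% type I error (sidedness not stated). The exact F test rejects when F/(1+2×0.9/0.1) = F/19 exceeds the critical value on 11 and 12 df. One-sided, that value is 2.717, so the observed ICC must reach (2.717×19−1)/(2.717×19+1) = 0.962. At a true ICC of 0.99 the factor is 1+2×0.99/0.01 = 199, and power is P(F > 2.717×19/199) = 98.4%. At 2.5% in one tail it is 96.7%. The claim of more than 90% is correct.

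**2. Can the ICC check stand in for the comparison?** Section 8.0 (Aim 2) gives Ktrans of "0.44±0.25 vs 0.23±0.10" per minute. With 6 per group, the overall mean is 0.335 and the total SD is √[(0.25²+0.10²)/2 + 0.105²] = 0.217. The log-scale variance is 0.315. Suppose tumour wCV is 10% both before and after correction (assumed, no improvement):

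- Raw scale: 0.217²/(0.217² + (0.10×0.335)²) = 0.977.
- Log scale, first removing 20% measurement error from the published spread: (0.315−ln 1.04)/(0.315−ln 1.04+ln 1.01) = 0.965.

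At ICC 0.965 to 0.977 the check passes in 55–80% of trials although nothing has improved. Conversely, if the ICC rises from 0.60 to 0.85, which nearly halves the within-SD, it passes in about 1%. At the documents' own wCVs it does separate the data sets: it passes in 2–8% of trials at 20% and in over 99% at 4%.

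**3. What would a comparison show?** Let d = ln(scan 1/scan 2), normal with SD √(2 ln(1+wCV²)), in 12 patients. The correlation between corrected and uncorrected d is assumed at 0, 0.4 or 0.8, since the documents give none. The pilot ICCs imply a within-SD reduction, at equal between-subject spread, of √(0.11/0.89)/√(0.01/0.99) = 3.5-fold.

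Three rules are compared:

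- *Separate intervals part.* The 95% limits for a within-SD on 12 df are 0.717 and 1.651 times the estimate, so the observed reduction must exceed 1.651/0.717 = 2.30-fold.
- *Unpaired two-sided 5% F test.* The observed reduction must exceed √F(0.975; 12, 12) = √3.28 = 1.81-fold.
- *Paired 95% interval about zero.* With d0 uncorrected and d1 corrected, w = Σd1²/Σd0², r² = (Σd0d1)²/(Σd0²Σd1²) and K = 1+2(1−r²)t²/(n−1), where t is the 97.5% point on n−1 df. The limits are √(w[K±√(K²−1)]). Improvement is claimed if the upper limit is below 1.

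Percentage of simulated trials claiming improvement (correlation 0/0.4/0.8, good to about one percentage point):

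| True change in wCV | Intervals part | Unpaired F | Paired interval |
|---|---|---|---|
| 20% to 4% (pilot wCV) | 99 or more | – | above 99.9 |
| 3.5-fold (pilot ICC) | 92 or more | – | 98 or more |
| 20% to 10% (assumed) | 31/29/20 | 62/64/70 | 62/68/93 |
| 20% to 12% (assumed) | 14/11/4 | 38/37/31 | 38/43/75 |
| none | 0.4 or less | – | about 2.5 |

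The paired interval covers the true ratio in about 95% of trials. Section 3.5 allows the second scan to be omitted. With 10 complete pairs the paired figures are 99.6–100% for 20% to 4%, 53–87% for 20% to 10% and 31–65% for 20% to 12%.

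**4. Reading the table.** At correlation 0 there is no pairing to exploit, yet non-overlap gives 31% and the paired interval 62%. The unpaired F test also gives 62%. Most of that gap is therefore the strictness of non-overlap, not lost pairing. Pairing adds materially only at high correlation (93% against 70% at 0.8).

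**The case against.** A comparison is planned, since the uncorrected %RDC is calculated for that purpose and ICC and %RDC are both named. Section 8.0 offers ICC above 0.9 as a sample-size justification and nowhere says that it settles the comparison. The study is a 12-patient pilot and this is its secondary goal. With either of the documents' own pilot effects the answer would be plain however the two data sets are compared. Every unfavourable result above uses an assumed wCV, and non-overlap of intervals is a comparator chosen for illustration that the plan does not propose.

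All of this stands, and it limits the weight of the point. It does not close the gap, because a descriptive comparison cannot support a goal stated as a significant increase.

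A reader might go further in three ways that the documents do not support:

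- *That 12 patients are too few, or Aim 1 is miscalculated.* Its power is confirmed, and 12 pairs give high power for a paired comparison at pilot-sized effects.
- *That separate intervals overlap because they ignore the pairing.* At low to moderate correlation the main cause is that non-overlap falsely claims improvement in 0.4% of trials or fewer, against 2.5% for the paired interval. The documents give no correlation.
- *That smaller reductions are likely in tumours.* They are stress tests. The documents give no glioblastoma wCV in either direction.

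**Conclusion.** The mismatch is real and modest. As written, the plan cannot say whether reproducibility was significantly increased, because its only sized criterion and its only planned interval do not concern the change. If a cut in within-SD of about 3.5-fold or fivefold carries over to tumours, there will be little practical harm. If the reduction is nearer twofold or less, the conclusion will depend on which comparison is chosen afterwards: for an assumed 20% to 10%, between 20% and 93% of trials would claim improvement, depending on rule and correlation.

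These sizes assume 12 complete pairs, normal log-differences, correlations from 0 to 0.8 and wCVs not taken from tumours. The gap itself rests on the text alone.

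**What to change.** In Section 8.0, name the secondary analysis as the paired corrected/uncorrected wCV ratio for Ktrans. This equals the %RDC ratio, since %RDC = 2.77 × wCV. Specify:

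- *Data:* ln(scan 1/scan 2), uncorrected and corrected, in patients with both scans. Section 8.0 makes log transformation conditional. For this relative measure, state that it always applies.
- *Interval:* two-sided 95%, Pitman-Morgan type, computed about zero so that a fixed scanner offset counts as error. This fits Section 3.1, where "The data reproducibility across two different scanners assesses between-scanner variability".
- *Rule:* claim a significant increase only if the upper limit is below 1.
- *Sensitivity:* a Wilcoxon signed-rank test on |ln(scan 1/scan 2)|.
- *Supportive:* keep ICC above 0.9 and its sample-size sentence.
- *Power, with its assumptions:* above 99% for 20% to 4%; 98% or more for a 3.5-fold reduction; 62–93% for an assumed 20% to 10%; 38–75% for an assumed 20% to 12%.

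The cost is a few sentences and one analysis of data already collected. There are two downsides. Power is limited for small reductions: a halving of wCV is missed in 7–38% of trials. The interval also relies on roughly normal log-differences, which 12 pairs cannot verify. With heavy tails (t on 5 df), coverage falls to 80–89% and false claims rise to 5.5–10%, while the Wilcoxon test stays at 2.1%. That test has less power under normality (40–71% for 20% to 10%), which is why it is proposed as a check and not as the decider.

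If the sponsor wants no inference in this pilot, reword Section 2.2 as estimating the change, drop the reference to significance, and report the same ratio with its interval.

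### The Aim 1 test (corrected ICC above 0.9) does not answer the secondary goal, which asks whether P4 correction increases reproducibility; a paired before/after test would

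*Combined protocol and SAP*

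**What the plan says.** The secondary goal (section 2.2) is to find out whether "the reproducibility of quantitative DCE-MRI measurement of glioblastoma can be significantly increased" when the P4 phantom is used to correct system-driven error.

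The sample size text for Aim 1 (section 8.0) starts from an earlier experiment in which Ktrans "reproducibility measured by the ICC was 0.99 in our previous experiment" after P4 correction. It then states the test to be powered: "to achieve greater than 90% power" and "to confirm that the data repeatability measured by the ICC is larger than 0.9 with 5% type I error", for which "at least 12 volunteers will be needed". It does not give the formula or the sidedness, and it does not say that 0.99 is the alternative.

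The statistical analysis text in section 8.0 plans a mixed model to "estimate the measurement error (within error) with two-sided 95% confidence interval", and lists ICC and %RDC as the reproducibility measures. Section 3.1 adds that %RDC (2.77 times wCV) will also be calculated without correction, for comparison. Neither place names a test of the difference.

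**The concern.** The goal and the powered test ask different things. The goal concerns a change within the same patients. The test compares one quantity, the corrected ICC, with a fixed number.

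The two would coincide only if uncorrected tumour data were known to lie well below 0.9. The plan gives no uncorrected ICC for tumour, and the figures it does give point to a value close to the bar. The mismatch works in both directions:

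- The corrected ICC could clear 0.9 although correction added little.
- Correction could bring a real gain and the test still miss the bar.

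At stake is whether the study can answer its own secondary goal with data it already plans to collect.

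**Working it through.** **1. The plan's own figure.** Inputs from section 8.0: bar 0.9, planning ICC 0.99, 5% type I error, power above 90%. Section 3.1 gives two scans per patient and the one-way ICC. With two scans, c(ICC) = 1 + 2·ICC/(1 − ICC), so c(0.9) = 19 and c(0.99) = 199. Exact power is P(F > Fcrit × 19/199), with degrees of freedom (n − 1, n), or (n − 1, n − 1) in the two-way form.

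- One-sided, (n − 1, n): 87.7% at 7, 91.7% at 8, 98.4% at 12.
- One-sided, (n − 1, n − 1): just under 90% at 8, 93.2% at 9, 98.0% at 12.
- Two-sided, (n − 1, n): 89.9% at 9, 93.0% at 10, 96.7% at 12.
- Two-sided, (n − 1, n − 1): 87.7% at 9, 91.5% at 10, 96.0% at 12.

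The strict minimum is therefore 8 to 10, and 12 meets the stated power in every variant. Power at 12 depends strongly on the true ICC. One-sided, it is 98% at 0.99, 85% at 0.98, 65% at 0.97 and 32% at 0.95.

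**2. Where uncorrected data may sit.** Section 1.0 gives an uncorrected ICC of 0.89 (four organs in three volunteers), and a wCV of about 20% before and 4% after correction. Section 8.0 gives tumour Ktrans of 0.44 ± 0.25 (true progression) and 0.23 ± 0.10 (pseudo-progression). For a 50:50 mix:

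- Mean = 0.335.
- Total variance = 0.5 × 0.10² + 0.5 × 0.25² + 0.25 × 0.21² = 0.0473.
- Error variance set at the overall mean = (0.20 × 0.335)² = 0.00449. ICC = 1 − 0.00449/0.0473 = 0.905 if the quoted SDs include error, or 0.0473/(0.0473 + 0.00449) = 0.913 if they do not.
- Error proportional to each value: variance = 0.04 × (0.335² + 0.0473) = 0.00638. ICC = 0.865 or 0.881.
- Log scale: 0.876 to 0.889.

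A 40:60 split gives 0.863 to 0.911. The overall range is about 0.86 to 0.91. With a 4% wCV the ICC is about 0.995 to 0.996.

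**3. A real gain that the bar would usually miss.** Suppose the ICC rises from 0.89 to 0.95. The ratio of within- to between-subject variance falls from 0.11/0.89 = 0.124 to 0.05/0.95 = 0.053, so within-subject variance is more than halved. By step 1, the test against 0.9 then has 32% power at 12 patients.

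**4. Power of a paired test.** For each patient, take the between-scan difference in log Ktrans before and after correction. The Pitman-Morgan test correlates the sum and the difference of these two values across patients (t with n − 2 degrees of freedom). Simulated at two-sided 5%, with normal differences and no constant offset between scanners:

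- wCV 20% to 4% (fivefold): over 99% power with 12 pairs, about 97% with 8.
- wCV 20% to 8% (2.5-fold): about 82% with 12 pairs if the before and after differences are uncorrelated, about 90% if their correlation is 0.5.

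**The case against.** The strongest reply is that the before/after comparison is already partly planned. Section 3.1 calculates the uncorrected %RDC, and section 8.0 attaches a two-sided 95% interval to the measurement error. That stands, and it narrows the gap to a missing test and missing power. However, two separate intervals set side by side ignore the pairing and give no decision rule for an increase.

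A second reply is that the uncorrected tumour ICC of 0.86 to 0.91 is derived. It borrows a wCV from volunteer organs, and most of the variants fall below 0.9. This also stands. It shows that the bar may be close to the uncorrected value, not that uncorrected tumour data already pass it. The argument does not depend on the exact value, since a one-sample test on corrected data cannot show a change.

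A reader might also infer from step 1 that the stated 12 is an arithmetic error. The documents do not support that. Method and sidedness are unstated, and 0.99 is rounded to two decimals. A value of 0.985 would need 11 patients one-sided or 13 two-sided by exact F, and 12 lies between them.

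**Conclusion.** The point holds as a mismatch between goal and test. The powered Aim 1 test does not address whether correction increases reproducibility, and its bar lies close to the documented uncorrected organ ICC of 0.89 and to the derived tumour range. The tumour range assumes that the 20% wCV transfers to glioblastoma.

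Twelve patients are not too few on the plan's own inputs. At ICC 0.99 they give about 96 to 98% power by exact F, so the figure is conservative rather than a minimum.

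A reader might go further and conclude that 8 complete pairs would be enough. That should not be written into the plan. With 8 pairs, one-sided power is 81% at a true ICC of 0.985 and 69% at 0.98, and the planning ICC comes from other organs in three volunteers.

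This is a low-severity point: an inexpensive improvement, not a flaw in the size of the study.

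**What to change.** - In section 8.0, make the Aim 1 test a paired comparison, in the same patients, of within-subject variability before and after P4 correction. Examples are a Pitman-Morgan test on the between-scan differences of log Ktrans, or a bootstrap confidence interval for the wCV ratio. Name one in advance.
- Say whether a constant offset between scanners counts as variability. Pitman-Morgan works on differences about their mean and leaves such an offset out. A wCV calculated from the raw squared differences includes it.
- State the power of that test at 12 pairs for the fivefold fall and for a smaller one, such as 2.5-fold.
- Keep ICC above 0.9 as a supporting result. Give its method, sidedness and alternative ICC, and replace the minimum with the power at 12 over a range of true ICC (one-sided: about 98% at 0.99, 85% at 0.98, 65% at 0.97).

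The cost is a few sentences and one extra analysis of scans already planned. Recruitment and sample size are unchanged.
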